### 6.2. Timing of Analyses

- After the completion of enrolling 24 subjects in Cohorts 1 and 2 (2 mg dose group), the SMC would review the data for Cohorts 1 and 2 through 7 days post the second vaccination.
- An interim analysis of safety, reactogenicity, and immunologic response data (excluding exploratory outcomes) was planned once all subjects (Cohort 1-4) have completed the Day 197 visit.
- The final analysis will be performed and a clinical study report completed when all primary safety endpoint data and all secondary immunogenicity endpoint data are available.
  - The CSR will be completed after the final data lock (through approximately Day 337 follow-up).
  - Any available data from the exploratory immunogenicity endpoints may also be included or if agreed upon, in an addendum to the CSR.

### 6.3. Analysis Populations

Summaries and analysis of safety data will be presented for the Safety Analysis Population. Summaries and analyses of immunogenicity data will be presented for the intent to treat (ITT) population. If there are major protocol deviations (as defined in Section 6.3.2) that result in the exclusion of data from at least 5% of all available visits across all groups, then a per-protocol (PP) analysis will also be performed for each immunogenicity end point.

#### 6.3.1. Intention-to-Treat Analysis (ITT) Population

The intent-to-treat (ITT) population includes all subjects who received at least one dose of study vaccine and contributed both pre- and at least one post-study vaccination venous blood samples for immunogenicity testing for which valid results were reported. Subjects will be grouped as randomized.

#### 6.3.2. Per Protocol Population

The per protocol (PP) population includes all subjects in the ITT subset with the following exclusions:

- Data from all available visits for subjects found to be ineligible at baseline.
- Data from all visits subsequent to major protocol deviations, such as:
  - Receipt of non-study licensed live vaccine within 28 days before or after study vaccination,

- Receipt of non-study licensed inactivated vaccine within 14 days before or after study vaccination,
- Receipt of immunosuppressive therapy (e.g., corticosteroids) within 30 days before or after study vaccination.
- Receipt of wrong study product.
- Data from any visit that occurs substantially out of window. See [Table 2](#) for visit windows.

### 6.3.3. Safety Population

The Safety Analysis population includes all subjects who received at least one dose of study vaccine.

### 6.3.4. Immunogenicity Population

The immunogenicity analyses will be performed for the ITT population. If there are major protocol deviations, as defined in Section [6.3.2](#), then a PP analysis may be performed.

## 6.4. Covariates and Subgroups

The protocol does not define any formal subgroup analyses, and the study is not adequately powered to perform subgroup analyses.

## 6.5. Missing Data

All attempts will be made to collect all data per protocol. As missing data are expected to be minimal, no imputation will be performed for missing values. Any data point that appears to be erroneous or inexplicable based on clinical judgment will be investigated as a possible outlier. If data points are identified as outliers, sensitivity analyses will be performed to examine the impact of including or excluding the outliers. Any substantive differences in these analyses will be reported.

## 6.6. Interim Analyses and Data Monitoring

After the completion of enrolling 24 subjects in Cohorts 1 and 2 (2 mg dose group), the SMC reviewed the data for Cohorts 1 and 2 through 7 days after the second vaccination. These reviews did not involve any hypothesis testing and will not be considered in estimating the precision of any estimates made at the conclusion of the study.

An interim analysis of safety, reactogenicity, and immunologic response data (excluding exploratory outcomes) is planned once all subjects (Cohort 1-4) have completed the Day 197 visit and the data are entered in the database, validated and monitored according to the clinical monitoring plan. The study statistician will provide the analysis of aggregate data unblinded at the group level to the investigators and sponsor staff for the purpose of manuscript, abstract preparation or presentation. The information from the primary immunogenicity and safety review may be published or otherwise presented, pursuant upon executed agreements between NIAID and VTEU investigators. The laboratory staff that run the assays for the Day 253 and 337 visits will remain blinded, and the assessment of relationship to study product of any SAEs that may be reported at the Day 253 and 337 visits will be delegated to blinded sub-investigators at the clinical site. While the results will not be used to make any decisions concerning the conduct of this trial, they may be used to make decisions on activities external to this trial such as the design of future trials of this vaccine. Since this early analysis of the data is not intended to impact the conduct of the trial, it has no impact on Type I error and adjustments are not planned.

---

All Tables and Figures to be included in the interim report are highlighted in Appendix 4 Interim Tables and Figures.

## **6.7. Multicenter Studies**

Not applicable. This study will take place at a single VTEU site (Cincinnati Children's Hospital).

## **6.8. Multiple Comparisons/Multiplicity**

This study was not designed to test any specific null hypothesis and, as such, no adjustments for multiple testing are planned.

## 7. STUDY SUBJECTS

### 7.1. Disposition of Subjects

[Table 15](#) will present a summary of the reasons that subjects were screened but not enrolled.

The composition of analysis populations, including reasons for subject exclusion, by vaccination group, will be presented in [Table 13](#). A listing of subjects excluded from each analysis population will be presented in [Listing 4](#).

The disposition of subjects in the study will be tabulated by vaccination group ([Table 12](#)). The table shows the total number of subjects that were screened, enrolled/randomized, received at least one treatment, received all scheduled treatments, completed all blood draws, completed Study Day 197 visit, completed follow-up (Study Day 337) and completed per protocol.

A flowchart showing the disposition of study subjects, adapted from the Consort Statement [\[12\]](#) will be included ([Figure 2](#)). This figure will present the number of subjects screened, enrolled, lost to follow-up, and analyzed, by vaccination group.

A listing of subjects who discontinued dosing or terminated from study follow-up and the reason will be included in [Listing 1](#).

Dates of first treatment administration by vaccination group will be presented in [Table 14](#).

### 7.2. Protocol Deviations

A summary of subject-specific protocol deviations will be presented by the reason for the deviation, the deviation category, and vaccination group for all subjects ([Table 4](#)). Deviations that are considered major deviations that will be reviewed for possible subject exclusion from the per protocol population include: receipt of non-study licensed live vaccine within 28 days before or after study vaccination, receipt of non-study licensed inactivated vaccine within 14 days before or after study vaccination (allowable exception for inactivated seasonal influenza vaccine received more than 7 days prior to or after a study vaccination), and receipt of immunosuppressive therapy (e.g., corticosteroids) within 30 days before or after study vaccination. All subject-specific protocol deviations and non-subject specific protocol deviations will be included in Appendix 3 as data listings ([Listing 2](#) and [Listing 3](#), respectively).

## 8. IMMUNOGENICITY EVALUATION

This study was not designed to test a specific null hypothesis; rather, the primary objectives include assessing the safety and tolerability of two dosages and two dose regimens of an ANDV DNA vaccine as compared to a placebo administration.

Immunogenicity and cellular assay data summaries and analyses will be presented by vaccination group for the ITT population, and for the PP population in the event of major protocol deviations (as defined in Section 6.3.2) or if any subjects are found to be ineligible at baseline. Summary statistics for continuous data will include mean, standard deviation (SD), median, minimum and maximum. For titer data, geometric mean and 95% CI will be calculated in place of arithmetic mean and standard deviation. Number of subjects, percentage (with denominator defined as the number of subjects with non-missing data), and exact (Clopper-Pearson) 95% confidence intervals will be presented for proportional endpoints.

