### 3.3. Study Definitions and Derived Variables

The term “vaccination group” refers to dose of study product and number of doses that subjects are randomized to receive. Therefore, there are five vaccination groups: ANDV DNA 2mg 3 doses, ANDV DNA 2mg 4 doses, ANDV DNA 4mg 3 doses, ANDV DNA 4mg 4 doses, and placebo. The placebo group will include all subjects who received placebo from all cohorts. Results will also be displayed for all subjects where indicated.

Seroconversion is defined as a post-vaccination ANDV-specific titer  $\geq 40$  if baseline titer  $< 20$  or a minimum four-fold rise compared to baseline if baseline titer  $\geq 20$ .

Geometric mean fold rise (GMFR) represents the geometric mean fold rise in antibody compared to baseline, calculated as the arithmetic mean of the difference in log antibodies back-transformed to the original scale.

Baseline is considered to be the last measurement taken prior to the first vaccination.

The lower limit of quantitation (LLOQ) for both PRT and PsVNA assay results is 20. Any values less than the LLOQ will be assigned a value of 14.1 by the lab. This imputed value will be used for the purpose of calculating summary statistics such as mean and GMT. All corresponding descriptive statistics that are  $< \text{LLOQ}$  will be reported as “ $< 20$ ” in summary tables.

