#### **4.3.3. Method of Assigning Subjects to Vaccination Groups (Randomization)**

Enrollment and randomization of subjects is done online using the enrollment module of Advantage eClinicalSM.

The first 24 participants in Cohorts 1 and 2 included two sentinel subjects. Sentinel subjects were randomized 1:1 to dose regimen and received 2 mg of study vaccine open label and were followed for safety through Day 8. Because there were no safety concerns, the 22 non-sentinel subjects in Cohorts 1 and 2 were randomized in a 9:2:9:2 ratio to receive either study vaccine or placebo at a dose of 2 mg in a 3 or 4 dose regimen, in double-blind fashion.

After successful SMC review, the 24 participants in Cohorts 3 and 4 followed the same schedule as outlined for Cohorts 1 and 2 above. Sentinel subjects received 4 mg of study vaccine open label and were followed for safety through Day 8. The remaining 22 non-sentinel subjects in Cohort 3 and 4 were randomized in a 9:2:9:2 ratio to receive study vaccine or placebo at a dose of 4 mg in a 3 or 4 dose regimen, in double blind fashion.

Subjects who withdraw, or are withdrawn or terminated from this trial, or are lost to follow-up after signing the ICF, randomization, and receipt of study vaccine will not be replaced.

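### When every titer in a cell is below 20, the planned GMFR confidence interval has zero width: 1.0 (1.0, 1.0) from 8 or 10 subjects

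*SAP*

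**What the plan says.** SAP 3.3 sets the floor: "The lower limit of quantitation (LLOQ) for both PRT and PsVNA assay results is 20" and "Any values less than the LLOQ will be assigned a value of 14.1 by the lab". It continues: "This imputed value will be used for the purpose of calculating summary statistics such as mean and GMT". The same section has a display rule, under which "All corresponding descriptive statistics that are" below the LLOQ are printed as <20. It defines GMFR on the log scale, "calculated as the arithmetic mean of the difference in log antibodies back-transformed to the original scale".

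SAP 8 gives the general rule for titers: "For titer data, geometric mean and 95% CI will be calculated in place of arithmetic mean and standard deviation". In its text SAP 8.2 ties confidence intervals to the GMT tables (27 to 30). The CI for GMFR comes from the shells of Tables 23 and 25, which Tables 24 and 26 repeat for the per-protocol population. Those shells include the placebo column and, for PsVNA, Day 29.

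I found no interval formula, no method for censored titers and no rule for a cell in which every value is below 20. Proportions get exact Clopper-Pearson intervals (SAP 8).

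**The concern.** An interval computed from identical values has no width. In a trial without hypothesis tests, the estimates and their intervals are the inference, and SAP 8.2 says that GMFR will be compared between groups. A printed 1.0 (1.0, 1.0) tells the reader that the absence of a rise is known exactly, when it rests on 8 or 10 people and an assay that cannot see below 20. In Tables 23 to 26 it would stand directly above a seroconversion rate of 0% whose exact upper limit is above 30%. The two lines would give contradictory accounts of the uncertainty in the same cell.

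Cells of this kind are plausible. Protocol 2.1 reports that nobody in a Baltimore-area study had detectable antibody to ANDV or SNV. The exclusion criteria also bar earlier hantavirus vaccination and ANDV exposure, so baselines should nearly all be below 20. Placebo has 4 PRNT GMFR cells (Days 57, 85, 169, 197) and 7 PsVNA cells (also Days 29, 253, 337).

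**Working it through.** **Inputs.** The LLOQ is 20 and the floor 14.1 (SAP 3.3). For group sizes, "the 22 non-sentinel subjects in Cohorts 1 and 2 were randomized in a 9:2:9:2 ratio", and Cohorts 3 and 4 follow the same scheme. With one sentinel each, an active group has 9 + 1 = 10 subjects, and the All column of a dose level has 20. Placebo is pooled ("The placebo group will include all subjects who received placebo from all cohorts"), giving 4 × 2 = 8. The true response rate p (titer 20 or more), the responders' titers and the interval formula are not in the documents. I assumed a range for p, lognormal responder titers (median 40 to 160 before truncation at 20, log10 SD 0.4) and a t interval on the log scale.

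**1. The plan's own figure.** Protocol Table 10 and SAP Table 3 use 1 − (1 − p)^n. For n=10 and p=10% this is 1 − 0.9^10 = 65.1%, as printed. All 18 entries reproduce.

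**2. Chance of a zero-width cell, baselines all below 20.** This is the complement, (1 − p)^n:

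| n | p=5% | p=10% | p=20% | p=30% |
|---|---|---|---|---|
| 8 | 66% | 43% | 17% | 6% |
| 10 | 60% | 35% | 11% | 3% |
| 20 | 36% | 12% | 1% | 0.1% |

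**3. What prints.** Each log difference is ln(14.1) − ln(14.1) = 0. The mean is 0 and the SD is 0, so GMFR = exp(0) = 1.0 with limits 1.0 and 1.0. Normal, t and bootstrap intervals all collapse, so the missing formula does not matter here.

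**4. What the data allow.** With zero responders the exact two-sided 95% upper limit is U = 1 − 0.025^(1/n): 36.9% for n=8, 30.8% for n=10, 16.8% for n=20. If a fraction U sat at titer T and the rest at the floor, GMFR would be (T/14.1)^U. For n=10 this is 1.4 at T=40 and 2.1 at T=160. For n=8 it is 1.5 and 2.5.

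**5. Coverage of the floored geometric mean by the nominal 95% interval (simulated).**

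| n | p=10% | p=20% | p=30% | p=50% |
|---|---|---|---|---|
| 8 | 56-57% | 78-81% | 86-89% | 91-94% |
| 10 | 64% | 82-85% | 88-90% | 93-94% |

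A zero-width interval at 1.0 cannot cover a true floored GMFR above 1.0, so coverage cannot exceed 1 − (1 − p)^n. At n=10 and p=10% that ceiling is 65.1%, and 64/65.1 is about 98%. Nearly all of the shortfall there comes from the zero-width cells. At p=30% the ceiling is 97.2%, so the remaining shortfall comes mostly from skewed data in small samples.

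**The case against.** - **The <20 display rule.** A reader might infer that the GMT intervals are equally misleading. They are not: an all-below-20 cell in Tables 27 to 30 would print as <20, which claims no precision. The rule does not sensibly apply to GMFR, which is a ratio, so the problem is visible mainly there.
- **Placebo.** A reader might infer that the placebo intervals are wrong. If true placebo response is zero and all baselines are below 20, the floored GMFR is exactly 1.0 and the interval contains it. What remains is that 8 subjects cannot establish this.
- **Low response is not a given.** Protocol 2.1 cites 30% and 40% for the first related vaccine trial. It also cites 56% for that trial's combined group, and 64% and 75% with another delivery system and two doses. Protocol 2.1.2 reports a higher GMT with jet injection than with needle in animals (349 versus 42). At 30% response the chance of a zero-width cell at n=10 is only 3%, and by 50% coverage is near nominal. The documents do not support a claim of severe under-coverage across the trial.
- **The exact intervals are already planned.** They are, with distribution curves and individual titers as well. This limits the harm, but it leaves the false interval in the table.
- **Lower limits below 1.0.** One responder at 40 among ten gives GMFR 1.11 (0.88 to 1.41). That is ordinary t-interval behaviour at a boundary. SAP 3.3 allows for baselines of 20 or more, so a population GMFR below 1.0 is not ruled out.

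**Conclusion.** The point holds in a limited form. Following the SAP as written, a cell with every titer below 20 at baseline and at the visit prints GMFR 1.0 (1.0, 1.0), whichever SD-based or bootstrap interval is used. The exact limits show that up to 36.9% (0/8) or 30.8% (0/10) true response is compatible with such data.

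The collapse itself needs no assumption beyond the data pattern. The coverage figures depend on the assumed response rates, responder titers and t interval. At n=10 the shortfall is severe at about 10% response, moderate at 20-30% and small by 50%. No test or decision rule depends on these intervals, so this is a reporting defect that should be corrected. It does not threaten the trial's conclusions.

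**What to change.** Add to SAP 8, with a matching footnote to Tables 23 to 26: when every titer in a cell is below 20 at baseline and at the visit, the GMFR CI is printed as NE and the reader is referred to the exact Clopper-Pearson CI for the proportion with titer 20 or more. Apply the same to the GMT CI in Tables 27 to 30 when every titer in the cell is below 20. The shells of Tables 19 to 22 show only counts and percentages, so the footnote should cite Figures 11 to 14 for that interval.

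Add a second footnote: GMT and GMFR intervals treat values below 20 as 14.1 and may under-cover when few subjects have quantifiable titers.

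The cost is one SAP sentence, a programming condition and two footnotes. The downside is that some cells show NE: by step 2, about 35% of n=10 cells at 10% response, 11% at 20% and 3% at 30%.

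I would not require two or more quantifiable titers before printing an interval. At n=10 that would blank 0.349 + 0.387 = 74% of cells at 10% response and 0.107 + 0.268 = 38% at 20%. In the n=20 columns, coverage of the intervals that remain would still be only about 92% at 30% response. Truncating the limits is not needed either.

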### 8.1. Primary Immunogenicity Analysis

Not applicable.

### 8.2. Secondary Immunogenicity Analyses

Summaries and analysis of immunogenicity data will be presented for the ITT population. If there are major protocol deviations (as defined in Section 6.3.2) or if any subjects are found to be ineligible at baseline, a per-protocol (PP) analysis will also be performed.

Immune responses in terms of a titer  $\geq 20$  in antibody post vaccination, measured by PsVNA and PRNT will be summarized. These results are presented in [Table 19](#), [Table 20](#), [Table 21](#), and [Table 22](#), and graphically in [Figure 11](#), [Figure 12](#), [Figure 13](#), and [Figure 14](#).

Geometric mean fold rise, incidence of seroconversion, and geometric mean titers (GMT) will be calculated and compared between groups at various time points for PsVNA and PRNT. GMFR and seroconversion results are presented in [Table 23](#), [Table 24](#), [Table 25](#), and [Table 26](#). GMT results along with 95% confidence intervals are presented in [Table 27](#), [Table 28](#), [Table 29](#), and [Table 30](#).

Reverse cumulative distributions (RCD) curves will be presented for PsVNA and PRNT antibody titers. Plots for each assay will be generated with three panels (for each measurement), and separate curves within each panel for each vaccination group, as shown in [Figure 3](#), [Figure 4](#), [Figure 5](#), and [Figure 6](#).

Box-and Whisker graphs of PsVNA and PRNT antibody titers will be plotted on a log scale over time, by vaccination group at each time point ([Figure 7](#), [Figure 8](#), [Figure 9](#), and [Figure 10](#)).

The Spearman correlation between PsVNA and PRNT titers will be evaluated and presented in [Table 31](#) and [Table 32](#). The correlation will be depicted in scatter plots as [Figure 15](#) and [Figure 16](#).

Data listings of PsVNA and PRNT assay results as reported by the laboratory will be provided in [Listing 7](#). Listings will be sorted by vaccination group, subject identifier (ID), and visit.

No formal hypothesis testing is planned.

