11 STATISTICAL CONSIDERATIONS

11.1 Study Hypotheses

This is a phase I, randomized, placebo controlled, double-blind, dose escalation trial and is not designed to test a specific hypothesis. Rather, it is intended to obtain preliminary estimates in healthy adults of the safety, reactogenicity, and immunogenicity of the ANDV vaccine in healthy adults.

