11.4.3.2 Immunogenicity (PsVNA, PRNT)

Summaries and analysis of immunogenicity data will be presented for the ITT population. If there are major protocol deviations, a per-protocol (PP) analysis may also be performed.

Immune responses in terms of a titer ≥ 20 in antibody post vaccination, measured by PsVNA and PRNT will be summarized. Analyses will include incidence of seroconversion at different time points and geometric mean titers for the different groups at the different time points will be determined and compared. The correlation between PsVNA and PRNT titers will be evaluated.

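### GMT, GMFR and seroconversion are to be compared between groups, but Tables 23-30 give no ratio or difference with its own confidence interval

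*SAP*

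**What the plan says.** Both documents commit to a between-group comparison of immunogenicity. SAP 8.2 states that GMFR, seroconversion and GMT, by PsVNA and PRNT, will be "calculated and compared between groups at various time points". Protocol 11.4.3.2 states that "geometric mean titers for the different groups at the different time points will be determined and compared". Neither names a contrast, an interval method or a priority comparison.

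The precision measures specified are all within group. SAP 8 says: "For titer data, geometric mean and 95% CI will be calculated in place of arithmetic mean and standard deviation". For proportions, "exact (Clopper-Pearson) 95% confidence intervals will be presented for proportional endpoints". The shells follow this. Tables 23-26 (GMFR and seroconversion) and Tables 27-30 (GMT) have one column for each of Cohorts 1 to 4, a pooled column for 2 mg, a pooled column for 4 mg, and placebo. Each cell holds an estimate and that column's own 95% interval.

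The trial is descriptive. Protocol 11.1 says it "is not designed to test a specific hypothesis", and SAP 8.2 closes with "No formal hypothesis testing is planned". SAP 6.8 plans no multiplicity adjustment.

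**The concern.** The plan announces a comparison and then specifies nothing that estimates one. A confidence interval for one group's GMT describes that group. The uncertainty of a dose or regimen effect is the uncertainty of a ratio or difference, and that quantity has no row, column or method anywhere in Tables 23-30.

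The design could supply it. The four vaccine arms form a two-by-two layout of dose (2 mg, 4 mg) by regimen (3 or 4 active doses), with 10 subjects per cell, so each factor can be estimated on 20 against 20. Dose at least has pooled columns to set side by side. Regimen is randomised within each dose level, yet it has no pooled column.

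SAP 2.1 and 6.6 say that the group-level results released after Day 197 may inform the design of future trials. Dose and number of injections are natural questions at that point, and the report would hold no direct estimate of either effect with its precision.

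**Working it through.** **The plan's own figure.** The only sample-size figures are in protocol Table 10 (SAP Table 3): the chance of seeing at least one adverse event, 1 - (1 - p)^n. For n = 10 and p = 5%, 1 - 0.95^10 = 40.1%. For n = 20 and p = 10%, 1 - 0.90^20 = 87.8%. All 18 entries reproduce. They concern adverse events and say nothing about comparing titers.

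**Inputs.**
- Each vaccine cohort has 9 randomised subjects plus 1 sentinel, so 10 (protocol Table 1). Two cohorts pooled give 20.
- The confidence level is 95% (SAP 8).
- The log10 titer SD is not given in either document. I assume 0.3, 0.5 and 0.7 to show a range, with equal SDs and normal log titers.

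**Observed GMT ratio needed under each reading.**
- Interval for the ratio excludes 1: log10 ratio > t(2n-2) × SD × sqrt(2/n).
- Two within-group intervals do not overlap: log10 ratio > 2 × t(n-1) × SD / sqrt(n).

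For SD = 0.5:
- 20 v 20, ratio interval: 2.024 × 0.5 × sqrt(2/20) = 0.320, or 2.09-fold.
- 20 v 20, non-overlap: 2 × 2.093 × 0.5 / sqrt(20) = 0.468, or 2.94-fold.
- 10 v 10, ratio interval: 2.101 × 0.5 × sqrt(2/10) = 0.470, or 2.95-fold.
- 10 v 10, non-overlap: 2 × 2.262 × 0.5 / sqrt(10) = 0.715, or 5.19-fold.

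| Groups | Reading | SD 0.3 | SD 0.5 | SD 0.7 |
|---|---|---|---|---|
| 20 v 20 | ratio interval excludes 1 | 1.56 | 2.09 | 2.81 |
| 20 v 20 | intervals do not overlap | 1.91 | 2.94 | 4.52 |
| 10 v 10 | ratio interval excludes 1 | 1.91 | 2.95 | 4.55 |
| 10 v 10 | intervals do not overlap | 2.69 | 5.19 | 10.0 |

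**Error rates.** With equal standard errors and large samples, non-overlap has a two-sided false-positive rate of 2 × (1 - Φ(1.96 × sqrt(2))) = 0.0056. In 300,000 simulated data sets it was 0.0055 for 10 v 10 and 0.0054 for 20 v 20, against 0.05 for the interval on the difference. At a true difference that the latter detects 80% of the time (1.325 SD for 10 v 10, 0.91 SD for 20 v 20), non-overlap detects 45% and 48%.

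**Seroconversion.** Take 8/20 against 15/20 as an illustration. The Clopper-Pearson intervals are 19% to 64% and 51% to 91%, which overlap. The difference of 35 points has a Newcombe 95% interval of 4 to 58 points (Fisher p = 0.054, so the evidence is borderline). For assumed true rates of 40% and 80%, exact enumeration gives the chance of a positive finding as 31% by non-overlap and 75% by the Newcombe interval at 20 per group, and 6% and 42% at 10 per group.

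**The case against.** The strongest reply is that the study is descriptive and that setting group estimates with intervals side by side is an ordinary meaning of comparing in a 48-subject phase 1 trial. Several parts of this stand.

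- A reader might infer that dose and regimen will be judged by interval overlap. No section says so and there is no decision rule. The overlap figures show what would happen if someone read the tables that way. If they did, the error would be to miss differences, not to create them.
- A reader might also infer that no comparison can be made from the tables. That goes too far. From n, the GMT and its upper limit, the standard error is log(upper/GMT)/t(n-1), and a ratio interval can be rebuilt unless the GMT is masked as below 20 under SAP 3.3. Seroconversion is tabulated with n, so a difference can be computed as well. Reverse cumulative curves, box plots and individual titers (Listing 7) are planned too, although Appendix 3 leaves listings out of the interim review.
- Protocol 3.2.2 defines the GMT outcome against baseline, and the GMFR rows deliver that with an interval. This does not cover the separate commitment to compare groups.
- The opening of SAP 8 contains the phrase "as compared to a placebo administration". It belongs to a sentence about safety and tolerability, so nothing here rests on it.

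The absence of hypothesis testing does not answer the point. A ratio or difference with a 95% interval is estimation, which protocol 11.1 gives as the purpose of the trial. Leaving the reader to rebuild it also means that the plan has not delivered what it announced.

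**Conclusion.** The point holds as a gap between text and tables. A comparison of GMT, GMFR and seroconversion is promised, and Tables 23-30 contain no between-group estimate or interval. The gap is widest for regimen, which has no pooled column. For dose, the pooled columns exist and only the ratio or difference is missing. The within-group intervals are correct for what they describe.

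If overlap were used in place of a contrast, the observed difference needed at 20 v 20 would rise from 1.56-2.81-fold to 1.91-4.52-fold over the assumed SD range, and the false-positive rate would fall from 0.05 to about 0.005.

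The titer figures depend on assumed SDs and on normal log titers. Values below 20 are set to 14.1 (SAP 3.3), and SAP 2 cites response rates of only 30% to 75% for related vaccines, so many values may sit at that floor. The figures are therefore approximate. This is a desirable improvement; it does not affect the primary safety objective or the conduct of the trial.

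**What to change.** Add one paragraph to SAP 8.2 that names the contrasts, limits them to the secondary time points (Days 57, 85 and 197) and labels them descriptive and unadjusted, without p-values.

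- **Regimen:** 4-dose v 3-dose, adjusted for dose level, at Days 85 and 197. This comparison is randomised within dose level.
- **Dose:** 4 mg v 2 mg, with regimens pooled at Day 57 and regimen-adjusted at Days 85 and 197. Pooling at Day 57 fits SAP 6.1, since that sample is drawn before the third injection. Add a note that this contrast is between sequentially enrolled cohorts.
- **Tables 23-30:** add GMT and GMFR ratios with 95% intervals back-transformed from log-titer differences, and seroconversion differences with score or exact 95% intervals.
- **Tables 19-22:** add differences in the proportion with titer at or above 20. That endpoint is reported there.

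The cost is more unadjusted descriptive intervals in a small trial. Dose on three days and regimen on two makes 5 contrasts; times 2 assays and 4 endpoints, that is 40 intervals for the ITT population, and twice that if the per-protocol analysis is run. No new data are needed.
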